1. STUDY RATIONAL

Diabetes is one of the largest medical challenges facing the world today. 12% of the world's health budget is spent on diabetes, that is USD 673 billion (Euros 585 billion). It is estimated that a lower limb is amputated due to diabetes every 30 sec. on a global scale, and it is known that 85% of all amputations are performed due to a diabetic ulcer¹. In Denmark 320.000 citizens has a diabetes diagnosis, an additional 200.000 are estimated to have diabetes unknowingly, and 750.000 to have the pre-stages of diabetes². These numbers have doubled in the past ten years and are estimated to cost DKK 86 million a day (or Euros 11.6 million a day)¹. One of the complications to diabetes is the "diabetic foot syndrome", which is a result of neurological abnormalities, vascular complications or a combination of the two. Knowledge about the causes of the disease has been gathered since the late nineteenth century³. In recent years, preventive therapy has been the focus of treatment, resulting in several national and international guidelines^{4,5,6}. Focus has been on education in self-care and awareness of risk factors, combined with "Foot-at-Risk" evaluation⁷, at least once a year and off-loading therapy crafted and applied by specialized personnel^{3,4}.

Steno Diabetes Center Copenhagen, University of Copenhagen, Denmark is a highly-specialized treatment facility focusing on the patient with diabetes. In spite of optimized treatment for patients with diabetes, and the fact that incidence of first time ulcers in patients with type 1 and 2 diabetes is declining, the incidence of first time ulcers is still 2.6 and 8.7 per. 1000 patient years for type 1 and 2, respectively⁸. Diabetic foot ulcers have a known association with increased mortality, morbidity and economic burden^{9,10,11}, at the same time most amputations in patients with diabetes are preceded by an ulcer¹².

Hammer, mallet and claw-toe deformities are some of the most common deformities associated with the *diabetic foot syndrome*. Prevalence has been reported between 32% and 46%^{13,14}. These deformities are predictors of diabetic foot ulcers^{15,16}. There are several theories on the etiology of hammer, mallet and claw toe deformities – the three classic deformities of the toes. In the diabetic patient setting, the classical theory is based on neuropathy (nerve damage associated with diabetes and other diseases), resulting in intrinsic muscle (muscles of the foot) dysfunction, changes that lead to imbalance between the flexor and extensor tendons, which in turn leads to hyperextension of the metatarsophalangeal (MTP) joint and/or flexion in the interphalangeal joints (IP), leading to the three classic deformities of the toes. The neuropathic theory is not sufficient to explain the full

scope of the problem, and other theories have been proposed¹⁷. In the non-diabetic patient, the neuropathic explanation is not viable, but the explanations still center on an imbalance between inand extrinsic musculature, resulting from deformities in the foot either as flexor-substitution or stabilization deformities¹⁸. The deformities change the pressure on the plantar aspect of the foot¹⁹. These changes in pressure make specific contact points predilection sites for ulcers. The sites have been described as tip of the toe ulcers, cock-up ulcers, kissing ulcers and plantar metatarsal ulcers²⁰.

The treatment of hammer, mallet and claw toe deformities in diabetes has classically consisted of offloading in the form of shoes, insoles and/or orthosis (i.e. silicone spacers, felt pads etc.) or flexor tendon tenotomy (cutting tendons) done by scalpel. Several studies on flexor tenotomies performed with scalpel have been performed^{21,22}; all have reported acceptable or positive results on ulcer healing and low complication rates, including one study from our own institute²³. At Diabetic Foot Study Group 2018 we presented unpublished results from a study showing that tenotomy done by needle has comparable results to the classical scalpel. However, no study has, to our knowledge, been published comparing conservative treatment with surgical approach to these deformities, let alone randomized controlled trials (RCT).

2. WHAT DOES THIS TRIAL ADD TO CURRENT KNOWLEDGE?

This is to our knowledge the first RCT looking at flexor tenotomies as a preventive treatment, and/or compared to conservative treatment. At the same time this is the first study looking at needle flexor tenotomies, as opposed to the classic tenotomies done by scalpel.

3. Hypothesis

We hypothesize that treating hammer, mallet and claw toe deformities in patients with type 1 and 2 diabetes, and impending ulcers (defined as nail changes, and hypercallosities at the predilection sites for ulcers associated with hammer, mallet and claw toe deformities) with needle tenotomy is a safe and effective treatment, and superior compared to offloading (conservative) treatment done by silicon spacer, insoles, felt, and/or therapeutic sandals

4. AIM

The aim of the RCT is to evaluate the effect of needle tenotomy when treating impending ulcers associated with hammer, mallet and claw toe deformities.

The study is designed as a prospective RCT comparing needle tenotomy with conservative treatment, for patients with deformities and impending ulcers associated with the three deformities. Primary endpoint will be number of new ulcers incurred, defined as ulcers associated with hammer, mallet and claw toe deformities, placed on treated foot.

Secondary endpoints will be complications: infections (defined as ailment associated with procedure or ulcer, that is diagnosed as infection by attending health professional), transfer lesions (defined as impending ulcers or actual ulcers at anatomical sites associated with hammer, mallet and claw toes in patients with diabetes, on non-treated hammer, mallet and claw toes after surgical treatment), minor amputations (defined as amputations below ankle level), major amputations (defined as amputations at or above ankle level).

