5.2 Patients

Inclusion criteria

- Patients aged 18 years or above
- Type 1 or 2 diabetes
- Hammer, mallet or claw toe deformity
- Impending ulcer associated with above mentioned deformities
- Able to understand written and oral information
- Ability to follow planned visits and treatment
- Able to provide informed consent in Danish and/or English

Exclusion criteria

- Revascularization procedure in the affected limb planned, or undertaken within the 4 weeks prior to screening
- Hammer, mallet and claw toe that are rigid in both MTP, IP joints
- Ulcer associated with hammer, mallet and claw toe deformities
- Toe pressure < 30mmHg
- Prior major amputations on affected or ipsilateral leg
- Other corrective operation is indicated to treat patients foot deformities as deemed by investigator
- Current treatment with cytotoxic drugs or with systemically administered glucocorticoids
- Treatment of foot ulcers with growth factors, stem cells or equivalent preparations within the 8 weeks prior to screening
- Likely inability to comply with the need for planned visits because of planned activity
- Participation in another interventional clinical foot ulcer-healing trial within the 4 weeks prior to screening
- Prior enrolment in this trial
- Judgement by the investigator that the patient does not have the capacity to understand the study procedures or provide written informed consent

Discontinuation of patients

- Patient discontinues assigned treatment for any reason, while not fulfilling one of the studies accepted endpoints
- Participants who withdraw from treatment will be asked to remain in the trial for follow-up, and data will continue to be collected and analyzed.
- Patient incurs a serious adverse event (SAE), defined as death or sepsis related to the study procedure

- Investigator decides to discontinue patient due to health or compliance reasons
- Patient misses 3 consecutive visits
- Patient misses 5 or more visits during the full treatment period

Patients who discontinue the study early will be invited to have a clinical visit before being discontinued.

Patients that are discontinued will revert to their normal treatment plan, and continue in their respective clinics.

Endpoints

- New ulcer incurred
 - When/if new ulcer is incurred pictures will be send to two external evaluators to be confirmed as new ulcer
- Patient reaches 12 month visit without incurring a new ulcer

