- Patient incurs minor or major amputation on either treated or nontreated limb
- Patient receives surgical intervention relevant for the study (other than planned in study)

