5.3.1 Needle Tenotomy Procedure

Patient is placed in seated posture with feet elevated. The toe(s) with hammer, mallet or claw toe deformity is anesthetized by a digital toe block with 1-5 ml of 1% lidocaine administered for each toe. The toe digital block is administered through a plantar approach, at the web level of the deformed toe(s), with a 0,6 mm diameter and 30mm long needle.

After anesthetizing the toe(s) the plantar aspect of the toe at web level is disinfected with an alcohol based disinfectant twice.

Both the long and short flexors are then severed with a 1.2mm diameter and 40mm long needle through a plantar approach, immediately proximal to the web level of the toe.

After the procedure a dry gauze bandage is applied and the patients treated foot/feet is/are elevated for 20 minutes to achieve haemostasis, and the bandage is checked for bleeding before discharge.

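### The primary outcome is defined in several ways, the triggers for the End visit conflict, and the plan does not say whether follow-up continues after End

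*Combined protocol and SAP*

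**What the plan says.** **Primary outcome.** Section 4 states that the primary endpoint "will be number of new ulcers incurred, defined as ulcers associated with hammer, mallet and claw toe deformities, placed on treated foot". The sample-size text in 5.8 again calls it a number of new ulcers, but its inputs are incidences of 10% and 6%, and the analysis list in 5.8 gives an incidence in the treated limb. Section 5.2 works per patient: a new ulcer is an endpoint, and so is "Patient reaches 12 month visit without incurring a new ulcer". It adds a confirmation step ("When/if new ulcer is incurred pictures will be send to two external evaluators to be confirmed as new ulcer") and names no foot. Section 5.3.1 allows for more than one foot ("the patients treated foot/feet is/are elevated for 20 minutes"), but no section says how two treated feet are counted.

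**Triggers for End.** Footnote 1 to the visit table in 5.4 ties End to any of the named endpoints. In 5.2 these include a new ulcer, "Patient incurs minor or major amputation on either treated or nontreated limb", and other relevant surgery outside the study plan. Section 5.5.4 restricts End to progression of the impending ulcer, or no progression by month 12.

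**After End.** Sections 5.4 and 5.5.5 schedule visits at 3, 6 and 12 months, counted from day 0. The only retention rule is in 5.2: "Participants who withdraw from treatment will be asked to remain in the trial for follow-up, and data will continue to be collected and analyzed". It covers withdrawal from treatment, not reaching an endpoint.

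**The concern.** A count of ulcers, a yes/no result per patient and an incidence per limb are different outcomes. They call for different analyses and sample sizes, and 5.8 names no test that would settle which is meant. With about nine patients expected to have a first ulcer (if 110 is the total), a few classification decisions could change the result.

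The conflict over End leaves sites without one rule on when that visit is held. No rule says how a patient with an amputation or other surgery before any ulcer enters the primary analysis.

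If visits stop at End, a count of ulcers is cut off there, and later infections, transfer lesions and amputations are not captured. More time is lost in the arm with more ulcers. If the trial's hypothesis holds, that is the control arm, so any tenotomy benefit on those secondary endpoints would be understated.

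**Working it through.** **1. Passages side by side**

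- *Two deformity-associated ulcers on one treated foot.* Section 4 counts two. Section 5.2 gives one patient-level event. The incidence in 5.8 could be read either way.
- *New ulcer on an untreated deformed toe of the treated foot, month 4.* It is a primary event under sections 4, 5.2 and 5.8. It triggers End under 5.4 with 5.2, but not under 5.5.4, which records ulcers unrelated to the registered impending ulcer as a separate item.
- *Minor amputation in month 2, no ulcer before it.* It triggers End under 5.4 with 5.2, but not under 5.5.4. No analysis rule exists.
- *Section 5.5.3.* It sends a patient to End if the impending ulcer progresses before week 10, and has patients report any ulcer arising between day 14 and month 3. Neither condition matches 5.4 or 5.5.4.

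**2. Follow-up lost if visits stop at End**

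Inputs: 10% and 6% (5.8). Assumptions: 110 is the total, split 55 and 55; visits stop at End; first ulcers are spread evenly over 12 months, so each costs 6 months on average.

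- Patients reaching End with an ulcer: 55 × 0.10 = 5.5 control; 55 × 0.06 = 3.3 tenotomy; 8.8 in all.
- Months lost: 5.5 × 6 = 33.0 and 3.3 × 6 = 19.8, out of 55 × 12 = 660 per arm, or 5.0% and 3.0%. The percentages are the same if 110 is per arm.
- Section 5.8 calls its incidence uncertain. At an assumed 20–30% control incidence with the same 40% relative reduction, the losses are 10–15% and 6–9%.
- The documents give no repeat-ulcer rate. If it is 1 to 5 times the first-ulcer rate (assumption), the uncounted ulcers at the plan's rates number about 0.3–1.5 in control and 0.1–0.5 in tenotomy.

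**3. Extra visits if collection continues**

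A patient ulcerating in months 0–3 has three scheduled visits left, in months 3–6 two, and in months 6–12 one. The average is 0.25 × 3 + 0.25 × 2 + 0.50 × 1 = 1.75. Expected visits are 8.8 × 1.75 = 15.4, and at most 8.8 × 3 = 26.4. If 110 is per arm, all these double.

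**4. The plan's own sample size, then power for an incidence**

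The plan's figure: 2 × (10 × (1.960 + 0.842) / 4)² = 98.1. This matches the stated 98, but as a number per arm. 98 / 0.9 = 109 and 99 / 0.9 = 110, in line with the stated 110. The text does not say whether 110 is per arm or in total, so both are shown.

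For a yes/no outcome at 10% against 6%, two-sided 5%, with mean proportion 0.08 (normal approximation):

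- Null standard error: √(2 × 0.08 × 0.92 / n). Alternative: √((0.10 × 0.90 + 0.06 × 0.94) / n). Power = Φ((0.04 − 1.96 × null SE) / alternative SE).
- n = 55 per arm: (0.04 − 1.96 × 0.0517) / 0.0516 = −1.19, so power is about 12%.
- n = 110 per arm: (0.04 − 1.96 × 0.0366) / 0.0365 = −0.87, so power is about 19%.
- n for 80% power: (1.960 × √(2 × 0.08 × 0.92) + 0.842 × √(0.10 × 0.90 + 0.06 × 0.94))² / 0.04² = 721 per arm.

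**The case against.** The strongest defence is that visits were always meant to continue. The visit table places follow-up after End, the follow-up dates run from day 0, and those visits include assessment of ulcer healing. Section 5.2 also lists endpoints separately from discontinuation, and only discontinued patients are said to return to usual care. This stands as far as it goes: a reader might infer that follow-up stops at the first ulcer, but the documents do not say so. They do not say the reverse either, and using the same visit to close ulcer-free patients at month 12 points towards stopping.

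A reader might also infer that ulcers on untreated toes (transfer lesions) drop out of the primary outcome, which would favour tenotomy. The documents do not support this. The definitions in sections 4, 5.2 and 5.8 all include such an ulcer on the treated foot, and new ulcers are an examination item at every visit from day 0. Only the visit trigger in 5.5.4 leaves it out. Overlap between a primary and a secondary endpoint is not exclusion.

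Two smaller objections hold. Foot against limb matters little, because toe-deformity ulcers lie on the foot. The month-3 limit in 5.5.3 sits in the day 7 and 14 section, so it shows only a missing self-report instruction for later ulcers.

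Finally, the power shortfall comes from using a two-means formula for an incidence, not from the wording about End. That is right. It belongs here only because settling on one outcome means the stated power must be restated for it.

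**Conclusion.** The point holds as a problem of definition. The primary outcome shifts between a count, a per-patient event and an incidence; the End rules contradict each other; and follow-up after End is left open. These should be settled before analysis.

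The follow-up loss is conditional on visits stopping, and it is small at the plan's own rates: 5% against 3% of patient-months, assuming equal arms and evenly spread ulcers. It becomes material only at higher incidences, which the documents do not give. No bias from omitting transfer ulcers is shown.

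If the outcome is an incidence of 10% against 6%, the stated 80% power is not delivered. It is about 12% with 110 in total and about 19% with 110 per arm.

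**What to change.** 1. State in 5.4 and 5.5.4 that outcome data collection continues at the existing 3-, 6- and 12-month visits after any endpoint. With 110 patients in total this costs about 15 expected visits at the plan's rates (at most about 27), and only wording if the visits were always meant to continue. Visits after amputation or surgery cannot be estimated from the documents. Section 7.3 lets controls be offered tenotomy after an ulcer, so data from then on should be described as including that crossover.
2. Use one primary outcome definition in sections 4, 5.2, 5.5.4 and 5.8, consistent with the incidence used for the sample size. One example is the first externally confirmed, deformity-associated ulcer by 12 months on a foot with a registered impending ulcer at inclusion, with either foot counting if both qualify. Report the number of ulcers per patient alongside it.
3. Reconcile 5.2, 5.4, 5.5.3 and 5.5.4 on what triggers End, and say how ulcers noticed between visits after month 3 are reported. State how amputation or other surgery before an ulcer enters the primary analysis.
4. Say whether 110 is a total or per arm, and restate the power for the chosen endpoint. This is the costliest consequence for the plan's claims, since 80% power for 10% against 6% needs about 721 per arm. The change reveals the shortfall and does not cause it.

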- Foot examination
 - Inspection of pressure point, and deformities
 - o Pulses
 - o Deformities
 - o New Ulcers

- Standard care & offloading
 - See section 5.3.2
- Tenotomy/conservative treatment application
 - The allocated treatment is performed
 - For details on tenotomy see section 5.3.1
 - For details on conservative treatment see section 5.3.2
- Impending ulcer evaluation
 - Anatomical placement
- Ulcer evaluation (if ulcer incurred)
 - Assessment of ulcer surroundings
 - Assessment of infection
 - Assessment of healing
- Measurement of longest length, width and depth in mm
- Measurement of area in mm³(length*width*depth)
 - Assessment of incision site (where applicable)
 - o Measurement of length, width and depth of ulcer(s) after debridement
- Categorizing by Texas Grading System
- Footwear assessment
 - Footwear and/or current offloading is evaluated
 - All patients in conservative and treatment group will be offered therapeutic sandals with customized insole at this visit
- Changes in medicine/new ailments
 - o Changes to the patient's medicine, and/or new diagnosis are registered

5.5.3 Visit Day 7, 14

The following is a specification of the above mentioned visits. If at any visit, before week 10, the impending ulcer has been deemed as progressed to active ulcer, patient is planned for end visit. If Patient incurs ulcer between visit day 14 and 3 month visit, patient contacts study personal to arrange end visit as soon as possible.

• Foot examination

- Inspection of pressure point, and deformities
- o Pulses
- o Deformities
- New Ulcers (not associated to registered impending ulcers)
- Changes in medicine/new ailments
 - o Changes to the patient's medicine, and/or new diagnosis are registered
- Standard care & offloading
 - See section 5.3.2
- Impending ulcer
 - Has impending ulcer progressed to active ulcer
- Ulcer evaluation (if relevant)
 - o Assessment of ulcer surroundings
 - o Assessment of infection
 - Assessment of healing
 - o Ulcer photo
 - o Measurement of longest length, width and depth in mm
 - Measurement of area in mm³(length*width*depth)
 - Assessment of incision site (where applicable)
 - o Measurement of length, width and depth of ulcer(s) after debridement
 - o Categorizing by Texas Grading System
- Footwear assessment
 - o Footwear and/or current offloading is evaluated
- Complications
 - Complications associated with tenotomy is registered (if relevant)
 - SAE is registered (if relevant)

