5.8 Statistics

All statistical analysis will be performed using the version of SAS currently used at our institute. All data will be analyzed on the intention to treat basis. All baseline data will be presented using appropriate summarizing statistics. Appropriate comparable statistical analysis will be applied to

- Incidence of new ulcer(s) in treated limb
- Mean time (in days) to healing of incision sites
- Incidence of minor amputations
- Incidence of major amputations

Odds-ratio will be applied to

- The incidence of secondary infection
- Pain in treated limb, associated with tenotomy
- Transfer lesion

Sample-size

The calculation is done with a Type 1 error rate (α) at 5%, and a power (1- β) at 80%. The primary endpoint is number of new ulcers incurred.

In the general diabetic population life time prevalence of diabetic ulcers has been reported at $15-25\%^{24}$, the yearly incidence in the same group is 6%. This study focuses on patients with a deformity reported to have a 1.5 hazard ratio²⁵, and signs of an impending ulcer like callus formation, which has been reported with a relative risk of 11^{26} . The incidence of new diabetic foot ulcers incurred by the study population is set at 10%, according to the above mentioned considerations.

The incidence in the intervention group (μ_A) is set at 6%, so the anticipated reduction in incidence is 4% compared to the incidence in the control group (μ_B) which as above mentioned is set at 10%. However, the numbers for incidence of new diabetic foot ulcers is an uncertain size, especially when looking at the specific group we are looking at, therefore the standard deviation (σ) is set at 10.

The calculator used is a 2 means, 2 sample, 2-sided equality calculator. The formula is

 $nB=(1+1/\kappa) ((\sigma z1-\alpha/2+z1-\beta)/(\mu A-\mu B))2$

nB= Sample size

 κ = The matching ratio

With the above described parameters, the sample size is 98 patients, which due to an expected dropout of 10% will be extended to 110 patients.

6. **Perspective**

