The results of these studies will allow us to evaluate if there's a clinical advantage to performing preventive tenotomies. Several studies have shown that tenotomies done by scalpel are safe, and that most patients go on to heal their ulcers, but none have compared tenotomies to standard care, and no studies have looked at tenotomies as a preventive treatment against new ulcers. Our hypothesis is that patients with impending ulcers associated with hammer, mallet and claw toe deformities will have a lower incidence of new ulcers associated with hammer, mallet and claw toe deformities. At the same time, unpublished data from our institute show that tenotomies done by needle has comparable results to tenotomies done by scalpel. The economic perspectives are vast if a preventive minimal invasive procedure, that can be performed in everyday clinical work, with a minimal surgical technique requirement, can lead to significant reductions in incidence of new ulcers.

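### The primary endpoint depends on an ulcer being associated with a deformity that only one arm has surgically treated, and no rule makes that judgement the same in both arms

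*Combined protocol and SAP*

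**What the plan says.** The only labelled definition of the primary endpoint is in section 4: "number of new ulcers incurred, defined as ulcers associated with hammer, mallet and claw toe deformities, placed on treated foot". Section 6 states the expected benefit with the same restriction: tenotomy patients "will have a lower incidence of new ulcers associated with hammer, mallet and claw toe deformities".

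Other sections word the outcome differently:

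- Section 5.2 lists the occurrence of a new ulcer as an endpoint, without restriction. Its confirmation step is that "pictures will be send to two external evaluators to be confirmed as new ulcer".
- Section 5.8 lists for analysis "Incidence of new ulcer(s) in treated limb". Its sample-size paragraph also names new ulcers as the primary endpoint without restriction.
- Section 5.5.4 ties the end visit to progression of the registered impending ulcer, or to its not having progressed by 12 months. Note 1 to the visit table in section 5.4 ties it to any named endpoint.

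Transfer lesions, a secondary endpoint in section 4, are impending or actual ulcers at deformity-related anatomical sites, but only "on non-treated hammer, mallet and claw toes after surgical treatment".

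Site-based wording exists elsewhere. Section 1 says: "The sites have been described as tip of the toe ulcers, cock-up ulcers, kissing ulcers and plantar metatarsal ulcers". Section 3 defines impending ulcers partly as "hypercallosities at the predilection sites for ulcers associated with hammer, mallet and claw toe deformities".

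**The concern.** Whether an ulcer is associated with a deformity is settled when the ulcer appears, after randomisation. Only the tenotomy arm has both flexors cut (section 5.3.1), as a treatment for these deformities. Deformities are re-inspected at each visit from Day 0 (sections 5.5.2 to 5.5.5), so whoever classifies the ulcer sees the toe as it then is. A control's toe has not been operated on, and an ulcer on it qualifies readily. The same ulcer on a toe that surgery has straightened can be judged unrelated to a deformity that is no longer there.

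Transfer lesions open a second route. An ulcer on an untreated deformed toe of the operated foot meets the primary wording, yet it also fits the transfer-lesion definition. No rule says whether it then still counts as primary. A control has no such alternative category.

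Both routes can only lower the tenotomy count. At stake is the treatment comparison itself, in a trial that plans on few events and describes no blinding.

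**Working it through.** **1. The wordings side by side.** Take a new ulcer under a metatarsal head of the study foot, away from the registered impending ulcer, in a tenotomy patient whose toe has straightened.

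| Section | Is it a primary event? |
|---|---|
| 4, by current toe shape | Can be ruled out |
| 4, by baseline deformity or anatomical site | Yes |
| 5.2 and 5.8 | Yes, no restriction |
| 5.5.4 | Does not itself trigger the end visit |

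In a control whose toe is still deformed, the same ulcer counts under both readings of section 4. The arms therefore differ only under the current-shape reading, and nothing in the text excludes that reading.

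**2. The plan's own figures.** Section 5.8 gives α 5% two-sided, power 80%, incidences of 10% and 6%, σ = 10 and dropout of 10%. The allocation ratio is not stated; I take 1:1.

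- n = 2 × [10 × (1.960 + 0.842) / 4]² = 98.1, which matches the stated 98. Rounded up, 99 / 0.9 = 110, which matches the stated total.
- The formula gives patients per arm, while the text uses 98 as the number of patients. That is a separate matter. Here it only sets the arm sizes: 49 per arm before the dropout allowance and 55 after it.
- Planned events at 55 per arm: 55 × 0.10 = 5.5 and 55 × 0.06 = 3.3, a difference of 2.2 patients.

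**3. Sensitivity to uncounted ulcers.** Assume the true incidence is 10% in both arms and a share m of tenotomy-arm ulcers is not counted. The observed tenotomy incidence is 10% × (1 − m). The last two columns give the exact binomial probability of a significant result favouring tenotomy, at 49 per arm and two-sided 5%.

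| m (assumed) | Observed, control vs tenotomy | Pooled z test | Fisher's exact test |
|---|---|---|---|
| 0 | 10% vs 10% | 3.0% | 0.9% |
| 10% | 10% vs 9% | 4.3% | 1.3% |
| 20% | 10% vs 8% | 6.1% | 1.9% |
| 40% | 10% vs 6% | 12.3% | 4.1% |

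The documents give no value for m. The 40% row is simply the share that reproduces the planned effect with no true effect, and it is not evidence that such a share would occur. Because the planned difference is 2.2 patients, reclassifying about two ulcers is enough to matter.

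**The case against.** The strongest reply is that the protocol uses association in an anatomical sense. Sections 1 and 3 speak of predilection sites, and the transfer-lesion definition in section 4 speaks of anatomical sites. Read that way, toe-tip and metatarsal ulcers count equally in both arms. The foot examination lists deformities but does not link them to endpoint classification. The visit question is whether the registered impending ulcer has become active, and its placement is recorded at inclusion and Day 0, so progression of that lesion is captured whatever the toe's shape. Section 5.3.1 describes cutting the flexors and does not say that the toe becomes straight.

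Much of this stands. Differential counting is a reading the text permits, not a rule it states. Three stronger inferences are not supported:

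- **That an ulcer on a straightened toe would be counted nowhere.** Sections 5.2 and 5.8 carry no restriction, and visits also record "New Ulcers (not associated to registered impending ulcers" (section 5.5.3).
- **That the external evaluators would rule such ulcers out.** They are asked only to confirm a new ulcer. No section says who decides association.
- **That a bias of a given size is shown.** Every value of m is an assumption.

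What the reply does not do is close the gap. The site-based sense is available, but the primary definition does not invoke it. Progression of the registered lesion is also narrower than the endpoint in section 4, which covers any deformity-associated ulcer on the foot.

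**Conclusion.** The concern holds as a weakness of definition, not as a demonstrated bias. The primary event turns on an attribution that one arm's treatment can change. It is made after randomisation, with no described blinding and no anchor to baseline deformity or site. The transfer-lesion category exists only after surgery and adds a second route in the same direction. Any resulting error would favour tenotomy, and its size is unknown.

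The sections also allow different primary outcomes: deformity-associated ulcers on the treated foot, any new ulcer in the treated limb, or progression of the registered lesion. That choice should not remain open once data are seen. A reader might conclude that the plan systematically excludes tenotomy-arm ulcers; the text does not say so. The conclusion rests only on the wording. The figures in the sensitivity table further assume 1:1 allocation, 49 per arm and an equal true risk of 10%.

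**What to change.** - Define the primary event identically in both arms: any new confirmed ulcer on the study foot at one of the four sites in section 1 (toe tip, cock-up, kissing, plantar metatarsal), whatever the toe's shape when the ulcer appears.
- Fix the study foot before randomisation, so that it has the same meaning in controls.
- State that an ulcer at these sites on a non-treated toe of the study foot counts as a primary event, whether or not it is also reported as a transfer lesion.
- Have the two external evaluators record only whether a new ulcer is present and at which site.
- Align sections 4, 5.2, 5.5.4 and 5.8 with this definition.
- Report any new ulcer on the study foot as a supportive analysis; the visits already record new ulcers.

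The cost is revised wording and one evaluator form, with no extra patients or visits. The downside is that a few ulcers at these sites unrelated to the deformity will enter both arms and dilute the effect slightly.
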